6.4.2 Sample Size Considerations

Given this is a pilot study, formal power analyses were not conducted. However, based on prior pilot data in which brief lab exposure to e-cigarettes were conducted by our group (HIC 2000025687) determined that 30 participants is sufficient to detect large differences of irritation and appeal by water concentration at two sided alpha level of 0.05.

6.5 Planned Analyses

6.5.1 Primary Objective Analysis

To examine the primary objective of the study, which is to examine how increasing the concentration of e-liquids with aldehyde flavor chemicals impacts sensory perception of irritation and appeal among current adult e-cigarette users, we will use mixed effects models with water concentration as the within subject factor and each of the measure (e.g. irritation, gLMS and appeal, LHS) as outcomes in separate models. A significant main effect of condition will be considered supportive of our hypothesis. We will construct confidence intervals for least square means and contrasts between least square means to estimate effect sizes and to inform future studies.

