Preliminary (unpublished) evidence from our chemistry lab at the Yale Tobacco Center of Regulatory Science (TCORS) have indicated that it may be possible to reduce acetal formation simply by adding water to e-liquids. This reduces acetal formation by shifting the chemical equilibrium of the formation reaction. Water is physiologically innocuous to inhale via e-cigarette and adding water to e-liquids may be an elegant way to reduce the sensory irritation and cytotoxicity of e-liquids that contain flavor aldehydes. However, adding water also inherently dilutes the flavor and nicotine concentration of the product, which may reduce the appeal overall. This could be a negative outcome if trying to use flavors as a tool to shift combustible cigarette users to potential reduced harm e-cigarettes. However, if irritation is reduced and appeal is not significantly reduced, a regulation requiring a fixed level of water to e-liquids could be a simple and effective tool to reduce potential toxicity in e-liquids with these flavors. *The goal of the proposed study is therefore to determine if the sensory irritation (a marker of potential toxicity) of commercial e-liquids, can be reduced by increasing their water content without adversely affecting flavor appeal in adult e-cigarette users.*

3 Rationale/Significance

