3.2.2 Potential Benefits

The proposed project will provide the FDA with important data regarding how adding an innocuous constituent, water, to e-cigarettes that contain flavors chemicals comprised of aldehydes, could have the ability to reduce user' irritation. E-liquids with flavor chemicals containing aldehydes are popular and common but may have potential associated toxicity that produces user experienced irritation. Preliminary data from our chemistry lab suggests adding water may be one way to reduce potential toxicity. Regulating the level of water in e-liquids is a relatively simple regulation for the FDA to implement. However, it is possible that adding water might negatively impact the potential value of these flavors for switching from combustible cigarettes by diluting flavorants and nicotine concentrations, potentially resulting in lower delivery (and thus appeal) per puff. Study outcomes could inform potential future legislation aiming at addressing certain health concerns of vaping products, such as a mandate for a minimum amount of water present in e-liquids.

An additional benefit in this study is to participants who are current THC/CBD vapers. They may be at additional risk for EVALI given their THC/CBD vaping, but are not currently being monitored. During the study, they will be monitored for EVALI related symptoms.

4 Study Objectives

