4.1 Hypothesis

We hypothesized that as total water volume is increased in nicotine e-liquids containing flavor aldehydes, sensory irritation experienced by the e-cigarette user will decrease. We do not expect to see this decrease in the control e-liquid (grape e-liquid), which does not contain flavor aldehydes.

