4.2 Primary Objective

The primary objective of this study is to examine whether (a) sensory irritation and (b) appeal are decreased in e-liquids containing flavor aldehydes (i.e. vanilla, cherry, cinnamon) compared to e-liquids not containing flavor aldehydes (i.e. grape) when the water concentration is increased from the baseline water concentration to the following levels; 5% total water volume, 10% total water volume, 20% total water volume.

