6.1.4 Method of Assignment/Randomization

All participants will receive every flavor/water concentration (4 e-liquids flavors at 4 water concentrations = 16 total manipulations). Participants and research assistants will be blinded to flavors administered. We will use block randomization to determine order flavors are presented in. Water concentration will be presented from hypothesized least irritating to most irritating (20% water, 10% water, 5% water, no alteration).

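### The hypothesis compares aldehyde flavors with grape, but the primary rule accepts any water main effect, so an effect shared by the grape control would count as support, or grape is not used at all

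*Combined protocol and SAP*

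**What the plan says.** - **Hypothesis (4.1).** Irritation will fall as water rises in the aldehyde liquids. For grape: "We do not expect to see this decrease in the control e-liquid (grape e-liquid), which does not contain flavor aldehydes".
- **Primary objective (4.2 and Synopsis).** The question is whether irritation and appeal "are decreased in e-liquids containing flavor aldehydes (i.e. vanilla, cherry, cinnamon) compared to e-liquids not containing flavor aldehydes (i.e. grape"), as water rises from baseline to 5%, 10% and 20%. Section 5.1 gives the non-aldehyde flavor the role of control.
- **Primary analysis (6.5.1, repeated in 6.4.1).** The objective is restated as "how increasing the concentration of e-liquids with aldehyde flavor chemicals impacts sensory perception of irritation and appeal", without grape. The method is "mixed effects models with water concentration as the within subject factor", one model per outcome. The criterion is: "A significant main effect of condition will be considered supportive of our hypothesis". Condition is not defined, no direction is given, and the text does not say whether grape data enter the model.
- **Secondary analysis (6.5.2).** Flavor is the factor, in separate models at each water level. The matching objective (4.3) covers differences among the aldehyde flavors.
- **Sample size (6.4.2).** Thirty participants are called sufficient for large differences by water concentration at two-sided 0.05, with no formal power analysis.

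**The concern.** The hypothesis is a difference between two water effects, one in the aldehyde flavors and one in grape. The decision rule looks at a single water effect. The plan can therefore report the aldehyde hypothesis as supported when water acts just as strongly in grape, which is the result the control was included to rule out.

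The documents supply two routes to such a shared effect:

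- **Dilution.** Section 2.2 says that "adding water also inherently dilutes the flavor and nicotine concentration of the product", and 3.2.2 expects an effect on appeal "by diluting flavorants and nicotine concentrations, potentially resulting in lower delivery (and thus appeal) per puff". Both apply to grape.
- **Order.** Section 6.1.4 fixes the sequence: "Water concentration will be presented from hypothesized least irritating to most irritating (20% water, 10% water, 5% water, no alteration"). Water level and bout number are thus confounded within every flavor.

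Section 3.2.2 says the results could inform legislation on a minimum water content, so it matters whether an effect is specific to aldehydes.

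**Working it through.** **1. Can any reading of the text supply the comparison?**

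- *Four flavors pooled:* the water main effect averages over flavors, so a shared effect satisfies the rule.
- *Aldehyde flavors only:* grape is absent.
- *Separate models by flavor (not stated):* finding significance in the aldehyde flavors but not in grape does not test a difference. With an equal effect of 0.5 SD in all flavors, that pattern still appears in about 35-54% of simulated trials, because grape has a third of the data.
- *The promised least-square-mean contrasts:* a model without flavor can compare only water levels.
- *Sections 6.5.3, 6.5.8 and 6.5.9:* none adds a flavor-by-water test.

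**2. The plan's own figure.** The n = 30 statement cannot be reproduced, because no power, SD, correlation or effect size is given. If large is taken to mean a paired standardized difference of 0.8, n = 30 has 98.9% power, and 80% power is reached at 0.53. So 30 is plausible for a water effect. The statement does not address the aldehyde-versus-grape contrast.

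**3. How often the rule declares support when the hypothesis is false.** All inputs are assumptions, in residual-SD units: subject SD 1, subject-by-flavor SD 0.7, between-subject SD of the native-to-20% slope (τ) 0, 0.5 or 1, equal steps between water levels, and the same effect d in all four flavors. The simulation used n = 30 and 6,000 trials per cell. The water test has 3 df with a subject-by-water error term. The contrast is a paired t on 29 df.

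| d | Pooled, τ = 0 / 0.5 / 1 | Aldehyde only, τ = 0 / 0.5 / 1 | Aldehyde minus grape |
|---|---|---|---|
| 0.3 | 50.3 / 41.5 / 30.0% | 38.0 / 33.5 / 26.5% | about 5% |
| 0.5 | 93.3 / 84.1 / 63.6% | 83.8 / 74.8 / 57.7% | about 5% |
| 0.8 | 100 / 99.9 / 95.2% | 99.9 / 99.3 / 92.4% | about 5% |

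With no water effect the water test rejects in 5-7% of trials.

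With only a random intercept for subject, the rates over both readings are 22-35%, 60-85% and 94-100%. If the subject-by-flavor SD is 1.5 and τ = 0, that model's rates drop to 2-3%, 22-36% and 89-97%, because leaving flavor out inflates the standard error.

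**4. Order and dilution.** A build-up of 0.1 SD per bout over the three steps from 20% to native gives 3 × 0.1 = 0.3 SD with no water effect at all, which is the first row of the table. For dilution, section 6.1.3 uses 1% native water as its example. Going to 20% leaves (1 − 0.20)/(1 − 0.01) = 0.81 of the original concentration. That takes 36 mg/ml nicotine to about 29 mg/ml (ignoring density), in grape as in the others.

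**5. Precision of the contrast.** Variance of the native-minus-20% change, in units of residual variance / n:

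- pooled: 2/4 + τ²
- aldehyde only: 2/3 + τ²
- aldehyde minus grape: 2/3 + 2 = 8/3 (a slope common to all flavors cancels)

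Ratio of the contrast's SE to the pooled SE: √(2.667/0.5) = 2.31, √(2.667/0.75) = 1.89 and √(2.667/1.5) = 1.33 at τ = 0, 0.5 and 1. Against aldehyde-only, the ratios are 2.00, 1.71 and 1.26.

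95% half-width of the contrast: 2.045 × √((8/3)/30) = 0.61 SD.

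Effect detectable with 80% power: 0.529 × √(8/3) = 0.86 SD, against 0.37-0.68 SD for the water effect. If the hypothesis is true, the contrast has about 16%, 37% and 74% power at 0.3, 0.5 and 0.8 SD.

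**The case against.** - **The aldehyde-only reading tests part of the hypothesis.** That is correct: it addresses the first sentence of 4.1. It leaves untested the expectation for grape and the comparison in 4.2, which is the primary objective.
- **The secondary models may include grape.** Section 6.5.2 does not restrict flavor to the aldehydes, so aldehyde-minus-grape could be estimated at each water level, and subtracting two such estimates gives the right point estimate. Separate models give no standard error or test for that difference, and 4.3 limits the aim to the aldehyde flavors.
- **The false-support rates depend on the model.** If flavors differ in mean irritation and the model has only a random intercept, rates at small effects fall. With assumed flavor means spread over 0 to 2 SD, they are 9-20% (pooled) and 6-13% (aldehyde only) at d = 0.3, and 52-59% and 40% at 0.5. At 0.8 they stay at 84% or more. This stands for small effects, and it comes from the same omission of flavor.
- **One control flavor is a weak control.** Grape may differ from the others in more than aldehyde content. Native water is measured per container (6.1.3), so the step to 20% may not be the same dilution in each flavor. Both limit interpretation of the contrast and should be acknowledged.
- **This is a pilot.** Low power is a reason to present the contrast as an estimate with its interval. It does not justify a significance rule aimed at a different quantity.

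**Conclusion.** The concern holds and must be fixed. Sections 4.1, 4.2 and 5.1 set up a comparison with grape. The rule in 6.4.1 and 6.5.1 does not test it on either reading, and no other section does. This conclusion rests on the text alone.

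The size rests on assumed SDs and effects. With a subject-by-water error term, a water effect common to all flavors would be declared supportive in roughly a quarter to a half of trials at 0.3 SD and in more than nine in ten at 0.8 SD. The contrast that matches the hypothesis rejects in about 5%. The rule also has no direction, so a rise in irritation with water would satisfy it.

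**What to change.** In 6.4.1 and 6.5.1, specify for each outcome one mixed model with water (four levels), flavor (four levels) and water × flavor as fixed effects, and random effects for subject, subject-by-flavor and subject-by-water. The subject-by-water term is needed: with subject and subject-by-flavor alone, the pooled water test rejects a true null in 5%, 7% and 16% of trials at τ = 0, 0.5 and 1. Session may be added, but not together with four-level flavor position. Flavors 1 and 2 are always in Lab 1 (6.1.7), so position determines session.

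Replace the main-effect sentence with wording such as:

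> Support for the hypothesis is a larger fall in irritation from native to 20% water in the aldehyde flavors (mean of cherry, vanilla and cinnamon) than in grape, with a 95% confidence interval excluding zero in that direction. The same contrast is reported with its interval at 5% and 10%, and for appeal.

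If another level or a joint test is to decide, name it in advance.

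In 6.4.2, limit the n = 30 statement to water effects and give the expected interval width of this contrast, using SDs from the prior pilot.

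State the limits. The contrast removes order effects only if they are equal across flavors: a build-up of 0.1 SD per bout in the aldehyde flavors alone would make it reject about 16% of the time.

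Two smaller points can go in the same amendment. Align 4.3 and 6.5.2 with the parenthetical in 5.2.2, which asks about differences in the effect of water; the water × flavor terms among the aldehyde flavors cover this. Reconcile the statement under 6.1.3 that nicotine concentration does not change with the dilution described in 2.2, 3.1 and 3.2.2.

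**Cost.** Only wording changes. Every participant already samples all 16 combinations (6.1.4), so no visits or data are added. An IRB-approved amendment is required (7.2, 7.13). The price is precision, so for this pilot the contrast is mainly an estimate with an interval.

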3.2 Purpose of Study/Potential Impact

The goal of the proposed study is to determine if the sensory irritation (a marker of potential toxicity) of commercial e-liquids containing aldehydes compared to a control non-aldehyde

containing e-liquid, can be reduced by increasing their water content without adversely affecting flavor appeal in adult e-cigarette users. Given that adding water to e-liquid is an innocuous manipulation, if irritation is reduced and effect on appeal is limited, this could be a tool for regulation to reduce harm associated with e-cigarettes.

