6.4 Statistical Method

6.4.1 Statistical Design

To examine the primary objective of the study, which is to examine how increasing the concentration of e-liquids with aldehyde flavor chemicals impacts sensory perception of irritation and appeal among current adult e-cigarette users, we will use mixed effects models with water concentration as the within subject factor and each of the measure (e.g. irritation, appeal) as outcomes in separate models. Outcome analyses will be intent-to-treat and using mixed-effects models. These models allow for different numbers of observations per subject, use all available data, and can handle missing-at-random data. If model assumptions will appear to be violated, we will transform the data or fit more flexible generalized linear or nonparametric mixed models. A significant main effect of condition will be considered supportive of our hypothesis. We will construct confidence intervals for least square means and contrasts between least square means to estimate effect sizes and to inform future studies.

For the secondary aim, which is to examine differences by flavor for outcomes at each water concentration, we will examine at each water concentration, flavor as the within subject factor and each of the measure (e.g. irritation, appeal) as outcomes in separate models. We will construct confidence intervals for least square means and contrasts between least square means to estimate effect sizes and to inform future studies.

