6.5.2 Secondary Objectives Analyses

For the secondary aim, which is to examine differences by flavor for outcomes at each water concentration, we will examine at each water concentration, flavor as the within subject factor and each of the measure (e.g. irritation, appeal) as outcomes in separate models. We will construct confidence intervals for least square means and contrasts between least square means to estimate effect sizes and to inform future studies.

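### The primary criterion, a significant water main effect, cannot be told apart from bout order and does not test the aldehyde-versus-grape comparison in the hypothesis

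*Combined protocol and SAP*

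**What the plan says.** The primary analysis appears in Sections 6.4.1 and 6.5.1. For irritation and appeal in separate models, "we will use mixed effects models with water concentration as the within subject factor". The decision rule is "A significant main effect of condition will be considered supportive of our hypothesis". Neither section names flavor, flavor class, a water-by-class term or bout order, and neither says whether grape ratings enter the model.

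Section 6.1.4 fixes the sequence: "Water concentration will be presented from hypothesized least irritating to most irritating (20% water, 10% water, 5% water, no alteration". Section 5.1 and Section 6.3 (Lab Visits) agree, and 6.3 says outright that water order is not randomized. Only flavor order is randomized. Section 6.1.1 conflicts with this, since it has the flavors and dilutions sampled in random order.

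Section 4.1 predicts that irritation falls with water in the aldehyde flavors, and says of the control: "We do not expect to see this decrease in the control e-liquid (grape e-liquid), which does not contain flavor aldehydes". The primary objective in Section 4.2 asks for a fall in irritation and appeal in aldehyde liquids "compared to e-liquids not containing flavor aldehydes (i.e. grape) when the water concentration is increased from the baseline water concentration". The secondary analysis is separate: "we will examine at each water concentration, flavor as the within subject factor". Section 3.2 gives the goal as finding whether irritation "can be reduced by increasing their water content without adversely affecting flavor appeal in adult e-cigarette users", while Section 2.2 warns that "adding water also inherently dilutes the flavor and nicotine concentration of the product, which may reduce the appeal overall".

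**The concern.** There are two faults, and each stands without the other.

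- **Order.** The most diluted liquid always comes first within a flavor and the undiluted one last. Irritation that builds up over bouts would look like a benefit of water. Desensitization would hide a real benefit. The main effect cannot tell these apart from water.
- **Comparison.** Suppose irritation fell equally in aldehyde flavors and grape. That contradicts Section 4.1, yet the rule would count it as support. If grape is pooled, the control contributes to the effect it should calibrate. If grape is left out, the control is unused. The secondary analysis does not repair this, because comparing flavors separately at each water level never tests whether the flavor difference changes with water.

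Dilution alone could also produce a common fall. Taking native water as 0% to 5% (an assumption), 36 mg/ml nicotine at 20% water becomes 36 × 0.80 / (1 − 0 to 0.05) = 28.8 to 30.3 mg/ml in every flavor.

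The study is meant to inform a possible water requirement for e-liquids, so crediting order or dilution to the aldehyde mechanism would matter.

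**Working it through.** **1. The plan's own figure.** Section 6.4.2 says 30 participants suffice for large differences at two-sided 0.05, and gives no power, SD or effect size. A paired t test with n = 30 has 98.8% power for a standardized difference of 0.8 and 75.4% for 0.5, and reaches 80% at 0.53. The statement is plausible for a water contrast, but it is not a figure that can be reproduced.

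**2. Aliasing.** Intercept, water (3 columns) and within-flavor position (3 columns) make 7 columns of rank 4, so position adds nothing to water. Score positions 0 to 3 (20%, 10%, 5%, native). Let β be the water slope and δ the drift per position, with subscripts A for aldehyde flavors and G for grape:

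- main effect with four flavors: (3β_A + β_G)/4 + δ
- main effect with three aldehyde flavors: β_A + δ
- aldehyde-minus-grape trend: (β_A − β_G) + (δ_A − δ_G)

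Only the last cancels a drift that all flavors share.

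**3. Support declared when water has no effect.** Assumed inputs: residual SD 1, subject-by-flavor SD 0.7, subject-by-water SD s = 0 or 0.5. Squared centered positions sum to 5. With K flavors, the 3-df water test has noncentrality 30 × 5 × δ² / (s² + 1/K), with denominator df 3(30K − 1) for s = 0 and 87 for s = 0.5. For example, K = 4, δ = 0.10, s = 0 gives 150 × 0.01 / 0.25 = 6.0. The last four rows are simulations of the model closest to the text: water as the only fixed factor, with a random subject intercept.

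| Drift, SD per bout (either direction) | 0.05 | 0.10 | 0.15 | 0.20 |
|---|---|---|---|---|
| Four flavors, s = 0 | 15% | 51% | 88% | 99% |
| Three aldehyde flavors, s = 0 | 12% | 40% | 76% | 96% |
| Four flavors, s = 0.5 | 10% | 26% | 55% | 82% |
| Three aldehyde flavors, s = 0.5 | 9% | 23% | 48% | 75% |
| Literal model, four, s = 0 | 6% | 31% | 74% | 97% |
| Literal model, three, s = 0 | 5% | 22% | 58% | 89% |
| Literal model, four, s = 0.5 (approx.) | 18% | 39% | 70% | 90% |
| Literal model, three, s = 0.5 (approx.) | 12% | 30% | 55% | 82% |

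**4. A real effect hidden.** Take β_A = 0.20, β_G = 0 and δ = −0.10. The four-flavor slope falls from 0.20 × 3/4 = 0.15 to 0.05, and the three-flavor slope from 0.20 to 0.10. Power drops from 88% to 15% (four) or 96% to 39% (three). With s = 0.5 it drops from 55% to 10% or 75% to 23%.

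**5. The contrast.** Its residual variance is 1 + 1/3, and subject-by-water variation shared by all flavors cancels. The trend SE is √(1.333/150) = 0.094 per level. Rejection stays at 5% under any common drift. If drift of 0.10, 0.15 or 0.20 occurs only in aldehyde flavors, rejection is about 19%, 36% or 56% (normal approximation).

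**6. Appeal.** Take a loss of 0.20 SD per level in all four flavors. The contrast has expectation zero and rejects 5%. The within-aldehyde trend has SE √(0.333/150) = 0.047 and detects the loss 98% of the time with no drift, 54% with δ = −0.10 and 5% with δ = −0.20 (87%, 34% and 5% with s = 0.5). Such drift could arise if wanting falls over bouts after the two hours of abstinence required in Section 6.3.

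**The case against.** The fixed order is a disclosed choice with stated chemosensory reasons (Sections 5.1 and 6.3). Bouts are only two puffs, 10 minutes apart, and participants are trained on the scales and on puffing first. Withdrawal ratings are also collected (Section 6.2.1). No document supports any particular drift size. All of this stands, and it is why the order itself is not criticized. Short bouts and waiting may shrink drift, but they do not remove the aliasing, and they do nothing about the missing grape comparison.

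Rates also depend on the model. At the smallest drift the literal model gives lower rates than the fuller one when s = 0 and higher ones when s = 0.5. From 0.15 SD upward every version gives 48% or more.

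The lack of direction in the rule is a lesser matter. Section 4.1 is directional and the planned least-squares contrasts would show the sign, so wording can settle it.

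The strongest objection is that build-up or desensitization may well be larger for aldehydes, which the protocol describes as irritants, than for grape. The contrast does not remove that part (step 5). It also costs precision. Both points stand, and they limit how firmly a 30-person pilot can conclude. They do not make the main effect a test of the stated hypothesis.

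**Conclusion.** The criterion is wrong as written and should be changed. That water is aliased with position, and that no test of the aldehyde-grape difference in water effect is planned, follows from the text alone and needs no assumption. The size does rest on assumptions, because the documents give no drift or SD. With n = 30 and no water effect, drift of 0.10 SD per bout leads to declared support in 22% to 51% of trials, and 0.20 SD in 75% to 99%. Opposite drift of 0.10 can cut power for a true effect of 0.20 SD per level from 88% to 15% with four flavors. The class contrast holds 5% under common drift only. For appeal, neither the contrast nor the within-flavor trend is enough by itself: the contrast cannot see a loss shared by all flavors, and the trend is confounded with order.

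**What to change.** 1. **Irritation (Sections 6.4.1 and 6.5.1).** Fit flavor, water and flavor-by-water. Base the conclusion on the aldehyde-mean-minus-grape difference in linear water trend, with scores fixed in advance, a 95% CI and the stated direction (less irritation with more water, relative to grape). Report the water main effect as confounded with bout order.
2. **Limits.** State that the contrast removes only drift common to all flavors. Add a sensitivity analysis with linear session bout (1 to 8) and separate aldehyde and grape slopes, and say that it assumes drift does not restart with each flavor. If drift does restart, in aldehydes only, at 0.10, 0.15 or 0.20 SD, it still rejects 11%, 18% or 29%. Its trend SE is 0.144, and power for 0.20 SD per level falls to 29%.
3. **Appeal.** Report the same contrast because Section 4.2 asks for it. Add within-flavor water contrasts with 95% CIs, labeled as confounded with order. State that a null aldehyde-minus-grape contrast is not evidence of preserved appeal.
4. **Order wording.** Reconcile Section 6.1.1 with Sections 5.1, 6.1.4 and 6.3, and correct the sentence in 6.3 that calls both ends of the sequence least irritating.

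The change needs an approved amendment (Sections 7.2 and 7.13) and should be settled before outcome data are examined. It needs no new data, visits or exposures.

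The price is precision. For native versus 20%, the contrast SE is √(2 × 1.333/30) = 0.298, against √(2/120) = 0.129 with four flavors (2.3 times) or √(2/90) = 0.149 with three (2.0 times). With s = 0.5 the ratios are 1.6 and 1.5. At n = 30, power for 0.20 SD per level is 54% to 56% by trend test and 40% by a 3-df test. It falls to about 42% by trend if subject-by-water variation is independent in the two classes (SD 0.5 each): SE √(1.833/150) = 0.111. Power of 80% by trend needs about 53 to 55 participants, or 0.26 to 0.27 SD per level at n = 30. In this pilot the contrast should be read mainly as an estimate with its CI.
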